2.4 Non-Clinical Studies: Pharmacology and Toxicology Studies

Native CC10 is produced primarily by non-ciliated respiratory epithelial cells and is the most abundant protein in normal adult lungs, constituting up to 7% of the total extracellular protein. Native CC10 is synthesized by a number of tissues including the lungs, pancreas, uterine endometrium, prostate, and seminal vesicles. The normal physiological tissue distribution for CC10 includes all

mucosal tissues except the eyes and central nervous system. The concentration of endogenous CC10 in the blood ranges from 10-120 ng/ml in normal, healthy adults and up to 5 µg/ml in patients with renal dysfunction. From the blood, CC10 enters numerous tissues and organs and is also excreted in the urine. Several studies have found significantly lower endogenous CC10 protein concentration and expression in the lungs of preterm infants who died or developed severe BPD, suggesting an integral role of this protein in normal lung homeostasis.

The CC10 protein has potent anti-inflammatory and anti-fibrotic properties as demonstrated by numerous *in vitro* and *in vivo* studies. Although there is no consensus as to the central mechanism of action, CC10 may mediate many of its short term anti-inflammatory effects through its role in vesicle and protein trafficking in Club (Clara) cells. Respiratory epithelial cells in CC10 knockout mice demonstrate a lack of secretory vesicles and the presence of unusual intracellular structures characterized by multi-layer stacked membranes and disproportionate amounts of Golgi, rough endoplasmic reticulum, and lysosomal compartments compared to respiratory epithelial cells from non-knockout mice. In the longer term, CC10 may mediate effects through development and/or maintenance of airway epithelial cells, including Club (Clara) cells (autocrine function), which secrete the majority of native CC10 in the lungs and circulation.

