2.5.2 Non-Therapeutic Studies of Human CC10 Physiology

Several studies have examined the concentrations of endogenous CC10 in premature newborn infants and found that CC10 concentration in pulmonary fluids is directly proportional to gestational age. A variety of methods have been used to detect and measure native CC10 in these studies including radioimmunoassay, ELISA, and LC-mass spectrometry. The consensus findings are that pulmonary CC10 expression and protein levels in lung fluids are low in ELGANS and increase over time with increasing gestational age. Rapid increases in CC10 levels in TAF occur following premature birth. No studies have been performed to document CC10 TAF levels in term infants with normal lungs. One study documented that CC10 mRNA is detectable in human fetal lungs as early as week 16, with the protein becoming detectable in amniotic fluid around week 22, and rapidly increasing after week 28 then plateauing at week 32 (~ 1 µg/ml; a pattern similar to surfactant proteins). Another study showed that CC10 levels are lowest in preterm infants who die or develop BPD compared to those who do not, and that a greater proportion of the native CC10 in patients who die or develop BPD is oxidized. It is notable that CC10 is also produced by the uterine endometrium and the placenta during the first and second trimesters of pregnancy, such that the fetus is exposed to CC10 throughout pregnancy and before the fetal lungs start producing it.

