4 STUDY DESIGN

This study is designed as a randomized, blinded, placebo-controlled phase 2 trial. The study will enroll premature infants with a gestational age of 24-29 weeks who are receiving positive pressure mechanical ventilation and surfactant replacement therapy for treatment of RDS. Placebo (normal saline) will be compared to two dose groups of rhCC10 as shown in Table 1:

TABLE 1: TREATMENT GROUPS FOR IT RHCC10 ADMINISTRATION

| Treatment | Route of Administration | Number of doses | Intratracheal Dose level |
|------------------|-------------------------|--------------------|--------------------------|
| Placebo (n = 44) | Intratracheal | 1, on day of birth | n/a |
| rhCC10 (n = 22) | Intratracheal | 1, on day of birth | 1.5 mg/kg |
| rhCC10 (n = 22) | Intratracheal | 1, on day of birth | 5 mg/kg |

The clinical study has a blinded, placebo-controlled design. The purpose of blinding the study is to minimize treatment bias while randomization offers each infant the possibility of receiving the study drug.

A total of 88 patients will be enrolled in three treatment groups in which high and low dose rhCC10 will be compared to placebo. A total of 44 patients will receive placebo, 22 patients will receive 1.5 mg/kg rhCC10, and 22 patients will receive 5 mg/kg rhCC10. Complete results of the study should allow direct comparison of three groups.

Patients enrolled in the study will meet the prescribing criteria for *Survanta* or *Curosurf* and will receive the usual recommended clinical dose of surfactant replacement therapy. Each patient will then receive a single IT dose of the study drug (or placebo) within four hours after surfactant. Patients may be given subsequent doses of surfactant if required, but will not receive additional doses of rhCC10.

Concentrations of rhCC10 will be evaluated in serum derived from the infant, umbilical cord, or placental blood before drug administration and in serum or plasma and urine on days 1 and 28, and 12 months CGA. TAF will be obtained on similar days if the infant is still intubated to evaluate the effects of a single IT dose of rhCC10 on native CC10 expression in the lungs. Total protein, TH2 cytokines, IL-6, and cellular infiltrates will also be evaluated in TAF samples, to the extent permitted by the volume of patient samples collected.

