| Mandatory TAF (CC10 & inflammatory markers) | X | | | | |
| TAF, if intubated (CC10 & inflammatory markers) | X | X | X | X | X |
| Urine (CC10 tests) | X | X | X | X | X |
| Stool (CC10 tests) | X | X | X | X | X |
| Blood spot for CC10 genotyping³ | X | | | | |

1. CC10 tests: CC10 ELISA, oxidized CC10 biomarker assay
2. Visit 1 CXR, if available. Further head ultrasounds and chest X-rays will be documented, if performed.
3. Blood spot for genotyping may be obtained at the time any sample is being collected for visits 1-5 and may be from scavenged blood.
4. All Visit 1 samples are baseline and should be taken BEFORE study drug is administered.
5. Day 1 = Day of birth

Following the initial dosing and 4 week follow up period is a 12-month follow up period (Period 2) which consists of regular monthly contact by cell phone or visits for assessments (as shown in Table 3). Visit 6 will occur 7 ± 1 days following Visit 5 on day 35 following birth. Visit 6 will also include documentation of vital signs, growth parameters, and physical examination. At the 12 month follow-up visit, a 0.5 mL blood collection will be performed to test for CC10 concentration and antibodies.

TABLE 3: SCHEDULE OF EVALUATIONS (PERIOD 2)

| Evaluation | Visit Number | | | | | | | | | | | | | | | |
|-------------------------------------|----------------|----------------------------|---------------|--------------|---------------|---------------|---------------|---------------|---------------|---------------|---------------|---------------|----------------|----------------|----------------|----------------|
| | 6 day 35 | 7 36 wk ² | 8 40 wk | 9 1 mo | 10 2 mo | 11 3 mo | 12 4 mo | 13 5 mo | 14 6 mo | 15 7 mo | 16 8 mo | 17 9 mo | 18 10 mo | 19 11 mo | 20 12 mo | 21 18 mo |
| TAF, if intubated (CC10 tests) | X | X | X | X | | | | | | | | | | | | |
| O ₂ challenge test | | X | | | | | | | | | | | | | | |
| Hearing screen | | X | | | | | | | | | | | | | | X |
| Bayley Infant ND Assessment | | | | | | | | | | | | | | | | X |
| 6 + 12 month interview & diaries | | | | | | | | | | | X | | | | X | X |
| Physical exam | X | | | | | | | | | | X | | | | X | X |
| Vital signs | X | X | | | | | | | | | X | | | | X | X |
| Growth data | X | X | | | | | | | | | X | | | | X | X |
| Eye exam data ¹ | X | X | | | | | | | | | X | | | | | |
| Discharge interview & summary | | X | | | | | | | | | | | | | | |
| Telephone visit | | | X | X | X | X | X | X | X | X | X | X | X | X | X | |

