Data will be summarized for the total cases and by treatment group with respect to: 1) baseline demographic and clinical characteristics and 2) efficacy and safety observations and measurements. Analyses will be conducted on both the intention-to-treat (ITT) and 'per protocol' cases. Between-treatment or between-group comparisons will be examined using chi-square tests (or Fisher's Exact tests when cell frequencies are small) for categorical outcomes and Student t-tests (alternatively, Wilcoxon Rank Sum Test) for scalar measures. Two-sided statistical tests will be conducted and the significance level will be set at 0.05 for each primary test. The efficacy and safety analyses will be conducted on both the ITT and per protocol population. ITT cases will be all randomized subjects who receive the study medication, while per protocol cases will be randomized subjects who complete the study (including all cause deaths) without any major deviations from the protocol procedures. Descriptive statistics will be used to detail the sample characteristics. Between-treatment arm

differences on key baseline demographic and clinical characteristics will be tested. This latter step will be used to identify potential pre-treatment covariates for subsequent secondary analyses. Key baseline variables include race, gender, length, weight, head circumference, SNAPPE-II score, and gestational age. Descriptive statistics for the total exposure to study drug during the treatment period (number of doses), timing of initial study dose, timing of discontinuation in the event of early termination, and rate of study dropout will be provided. Between-treatment differences will be tested using the statistical methods described earlier. Concomitant medications will be summarized by therapeutic/pharmacological class and treatment group. In addition, they will be listed by treatment group, name of drug, dates administered, dose, frequency and indication.

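### The CC10 and inflammatory marker data fall by default under an unadjusted t-test or Wilcoxon test; a parsimonious log-scale ANCOVA for blood markers, with tracheal aspirate results labelled descriptive, would be a small improvement

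*Combined protocol and SAP*

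**What the plan says.** **Samples.** Section 4 states: "Concentrations of rhCC10 will be evaluated in serum derived from the infant, umbilical cord, or placental blood before drug administration". It then lists serum or plasma and urine at days 1 and 28 and at 12 months corrected age. TAF is taken on similar days from infants still intubated, for native CC10, total protein, cytokines and cells. Section 6.1 includes blood and TAF in the baseline examination. Note 4 to Table 2 in section 6.4 says: "All Visit 1 samples are baseline and should be taken BEFORE study drug is administered".

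**Analysis.** Section 8.5 gives one rule for continuous measures: "Student t-tests (alternatively, Wilcoxon Rank Sum Test) for scalar measures". It adds: "Two-sided statistical tests will be conducted and the significance level will be set at 0.05 for each primary test". Sections 8.1 to 8.4 do not list the markers as endpoints. The only outcome models in section 8.5 are the logistic and Cox models for the efficacy endpoint.

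**Covariates.** Section 8.5 tests the arms for baseline differences and says: "This latter step will be used to identify potential pre-treatment covariates for subsequent secondary analyses". The candidates are given as: "Key baseline variables include race, gender, length, weight, head circumference, SNAPPE-II score, and gestational age". No pre-dose marker value is named. Section 5.3 stratifies by gestational age group, as well as by site and cohort, and promises to take account of any discrepancy in birth weight or gestational age, without naming a method.

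**Biology.** Section 2.5.2 reports that "CC10 concentration in pulmonary fluids is directly proportional to gestational age".

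**The concern.** The trial plans to collect a pre-dose value for each marker and stratifies on a variable that its own background ties to CC10 in lung fluid. An unadjusted test leaves both sources of between-infant spread in the error term. Screening for imbalance does not solve this: the gain in precision depends on how strongly a covariate predicts the outcome, not on whether the arms happen to differ, so a well-balanced trial would get no adjustment. With no method named, the scale and covariates could also be chosen after the data are seen.

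At stake are the marker estimates from this trial. Section 2.6 raises possible transient suppression of native CC10 and promises close monitoring, and section 8 says that observed trends will inform the next study.

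**Working it through.** **1. The plan's own power figure.** Inputs from section 8.5: 0.57 v 0.27, 44 per group, two-sided 0.05. The mean proportion is 0.42.
- SE under the null: √(2 × 0.42 × 0.58 / 44) = 0.1052.
- SE under the alternative: √((0.57 × 0.43 + 0.27 × 0.73) / 44) = 0.1003.
- z = (0.30 − 1.96 × 0.1052) / 0.1003 = 0.935, so power is 82.5%.

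The stated 82% reproduces. It concerns the binary primary endpoint, which this point does not touch. The documents give no effect size, SD or power for any marker.

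**2. Assumed marker inputs.**
- Spread: section 2.4 says "The concentration of endogenous CC10 in the blood ranges from 10-120 ng/ml in normal, healthy adults". Read as a 95% range of a log-normal variable, this gives log SD = ln(120/10) / 3.92 = 0.63. It comes from healthy adults, so it is only a stand-in for preterm infants.
- Effect: geometric mean ratio 0.6, so the log difference is |ln 0.6| = 0.511.
- Size: 20 infants per arm with a usable value.
- R² (share of log variance explained by the covariates): 0.04, 0.10 and 0.40.

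**3. Unadjusted tests.**
- Log t-test: noncentrality 0.511 / (0.63 × √(2/20)) = 2.56 on 38 df, power 70%.
- By simulation on the same inputs: raw-scale t-test about 63%, Wilcoxon about 68%.

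**4. Log ANCOVA with k covariates.** Multiply the SD by √(1 − R²). Multiply the noncentrality by √((37 − k)/37) for chance covariate imbalance, and use 38 − k df.

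| R² | k = 1 | k = 2 |
|---|---|---|
| 0.04 | 71% | 70% |
| 0.10 | 74% | 73% |
| 0.40 | 89% | 88% |

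Simulation agrees to within a point or two (73-75% at 0.10, about 88% at 0.40).

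**5. Separating the two gains.** Moving from the raw to the log t-test takes power from 63% to 70% with no covariate. Adjustment at R² = 0.10 then adds about 3 to 5 points, and at R² = 0.40 about 18. Against Wilcoxon, which section 8.5 already allows, the log scale alone adds about 2 points.

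**6. Too many terms.** With the baseline value plus four uninformative covariates, 20 per arm and R² = 0.10, simulated power is 68%, the same as Wilcoxon. With 8 per arm (assumed, to mimic a small intubated subset) it is 23%, against 31% for Wilcoxon and 33% for the log t-test.

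**The case against.** The case against making much of this is strong, and most of it stands.

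- **The method is inferred.** A reader might infer that the plan assigns the markers to a t-test. It does not: they are unlisted measures caught by a generic sentence.
- **Gestational age is not ignored.** A reader might infer that it is. It is a stratum, it is on the list of key baseline variables, and section 5.3 promises to consider imbalance. What can fairly be said is that this route is secondary, driven by imbalance and without a named model.
- **Other mechanistic evidence exists.** A reader might take these data as the drug's only mechanistic evidence. Sections 2.3 to 2.5.1 describe knockout-mouse and injury-model work, and reductions in aspirate protein and cells in the first infant trial.
- **R² may be low for blood.** Section 2.5.2 links gestational age to CC10 in pulmonary fluids, not serum. Pre-dose blood may be cord or placental, and that section says the placenta produces CC10 earlier in pregnancy. Such a baseline may predict an infant's later serum value poorly.
- **Precision is not the main TAF problem.** Section 6.4 limits day 28 TAF to infants still intubated. Intubation status after dosing is a post-randomisation event, so the arms compared are selected subsets, and baseline ANCOVA does not remove that selection. Numbers may also be very small: section 2.6 reports 2-3 day-3 samples per group in the first trial.

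None of this gives the pre-dose values a use or supplies a named marker analysis. It does limit the remedy to a small model and the claim to a minor one.

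**Conclusion.** The point holds as a minor, exploratory improvement. The only analysis that reaches the markers is unadjusted, the planned baseline values have no role, and adjustment for gestational age depends on observed imbalance.

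Under the stated assumptions, power goes from 68% (Wilcoxon) to about 73-75% at R² = 0.10 and 88% at R² = 0.40, with little or no gain near R² = 0.04. A reader might credit the whole distance from the raw t-test's 63% to baseline adjustment; about 7 points of it come from taking logs. Effect, spread, sample size and R² are all assumptions, so the direction is firmer than the size. For TAF, adjustment could even lose power if the model is large, and it cannot restore the randomised comparison.

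The primary analysis, the 82% power and the sample size do not change.

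**What to change.** Add one paragraph to section 8.5:

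- **Name the markers and post-dose visits.** Section 4 lists day 1 separately from the pre-dose sample, while section 6.4 and Table 2 make day 1 the baseline. Reconcile these so that the post-dose time points are clear.
- **Blood markers.** Analyse the log value at each post-dose visit by ANCOVA with treatment, log pre-dose value and gestational age only. Report the ratio of geometric means with a 95% CI. State in advance how a missing pre-dose value is handled.
- **Sensitivity analyses.** Keep Wilcoxon. Record whether the pre-dose blood was infant, cord or placental, and examine source here rather than through extra terms in the main model.
- **TAF markers.** Use log values, with at most one baseline covariate when few infants remain intubated. Report how many infants per arm contribute at each visit. Label the results descriptive because of the intubated-only selection.

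The cost is a paragraph of text and one case report form field for blood source, with no extra samples. The downside is a log-scale model assumption and a small loss of degrees of freedom.

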5 SELECTION, ENROLLMENT & WITHDRAWAL OF STUDY SUBJECTS

5.1 Inclusion Criteria

Newborn infants will be considered for the study if the following criteria are met:

- Age \leq 24 hours;
- Birthweight between 600 and 1,250 grams;
- Gestational age 24-29 weeks (not less than 24 weeks); at birth based on best estimate using obstetrical sonography (first or second trimester), solid dating criteria, or Ballard examination;
- Birthweight appropriate for gestational age;
- 5 minute Apgar score >5 (ie. 6-10);
- Diagnosis of neonatal RDS based on clinical and/or radiographic criteria;
- Requiring intubation and mechanical ventilation for treatment of RDS;
- Received at least one dose of surfactant (prophylaxis or rescue) or the decision to treat with surfactant has already been made (e.g. infant is intubated or in the process of being intubated and/or surfactant has been prescribed); and
- Written informed consent is obtained from the infant's parent or legal guardian prior to enrollment of the patient and agrees to all study-related procedures and evaluations, including those required after hospital discharge.

5.2 Exclusion Criteria

Patients meeting the inclusion criteria will not be eligible for the study if any of the following are present:

- 5 minute Apgar score of ≤ 5 (ie. 1-5); except in cases where the subject's Apgar score is ≤ 5 at 5 minutes, normalizes by 10 minutes, no acidosis is present on cord blood gas and the neonatal depression is thought to be due to maternal anesthesia or other drug exposure such as MgSO₄.
- Major congenital abnormalities (chromosomal, renal, cardiac, hepatic, neurologic, or pulmonary malformations; minor anomalies such as cleft lip/palate are permitted);
- Evidence of severe neonatal depression (as defined by cord blood pH ≤ 7.00 and/or an Apgar score of < 4 at 10 minutes);
- Evidence of congenital infection (bacterial or non-bacterial);
- Requires a major surgical procedure prior to administration of Study drug
- Enrollment in any other study involving administration of another investigational drug;
- Any condition which could preclude receiving study drug or performing any study-related procedures;
- Use of postnatal corticosteroids prior to administration of rhCC10, except as specified in the protocol;
- Use of inhaled nitric oxide prior to administration of rhCC10;
- Mother is known to be seropositive for HIV or HTLV-1 (per maternal medical records);
- Parent or guardian is unable or unwilling to complete the study diary after hospital discharge;
- Parent or guardian is unable to bring the infant back to the study center for follow-up evaluations after discharge.

5.3 Randomization

As previously described, two dose levels will be evaluated against the placebo in two consecutive cohorts. The first cohort will randomize patients to receive either 1.5 mg/kg or placebo. The second cohort will randomize patients to receive either 5 mg/kg or placebo. Each cohort will randomize 44 infants to either placebo or drug treatment. The overall design is 2:1:1; 44 (placebo):22 (1.5 mg/kg):22 (5mg/kg). The randomization scheme was developed and is maintained by StudyTrax, a secured electronic data capture platform that is compliant with 21 CFR-11 and HIPAA. A randomization ID is generated when a subject is randomized using the format TMC-001, BWH-002, and

so on (i.e. 3 letter site designation and three numbers designating the sequence in which the patient was enrolled). The randomization scheme uses the permuted block randomization method, with stratification by site and by gestational age group (divided into 24-27 wks CGA and 27-29 wks CGA), with block sizes 2,2,4. For Cohort 1, treatment groups are: Placebo and 1.5 mg/kg. When Cohort 1 is completed, Cohort 2 treatment groups will be: Placebo and 5.0 mg/kg. Cohort is also listed as a Stratification factor so that when Cohort 2 starts, any open blocks from the first cohort will not be filled. The Cohort is automatically set to 1 at the start of the study. Once Cohort 1 is done and Cohort 2 starts, that will change. Each site's pharmacy will receive authorization to access the patient randomization assignment via the Internet on StudyTrax.

The randomization assignment must not be disclosed to anyone outside the pharmacy. Patients who meet the inclusion criteria and are successfully enrolled will be assigned a patient Randomized ID number. Due to the time critical nature of managing the respiratory support of the subject and dosing with study medication, it is permissible for the patient to be randomized before receiving the first dose of surfactant. The patient Randomization ID number and the birth weight of the patient will then be communicated to the pharmacy on a paper form requesting study medication. The pharmacist will then access the StudyTrax randomization assignment on the Internet. The patient will be assigned to one of the three groups (placebo, low dose or high dose) as appropriate to the cohort, and an opaque syringe containing an appropriate dose of the study drug or placebo will be sent to study personnel in a sealed envelope. In order to administer the study drug within 4 hours of surfactant administration, the patient's birth weight should be communicated to the pharmacy as soon as it is available. The syringe received from the pharmacy will be identified only with the patient Randomization ID number and will contain 1.5 – 3.1 mL of solution, depending on the birth weight of the patient. StudyTrax will hold the key to patient treatment assignments, which will not be disclosed until the end of the study.

Given the small size of the study and the simple randomization scheme, it is possible that a significant discrepancy may exist among the treatment groups in birth weight and/or gestational age. Any such difference will be taken into account in evaluating the results of the study.

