2.2 Study Drug

The study drug, rhCC10, is a recombinant version of natural human CC10 protein. Native CC10 is produced primarily by non-ciliated respiratory epithelial cells, called Club (Clara) cells and is the most abundant protein in the mucosal fluids in normal healthy lungs. CC10 circulates in the blood and is excreted in the urine. The recombinant version is nearly identical to the native protein and shares all biological properties with the native protein that have been characterized thus far. rhCC10 is produced in *E. coli* bacteria.

The rhCC10 drug formulation to be used in this study is a clear, colorless liquid formulated in unbuffered normal saline (0.9%) at a concentration of 5.5 mg/ml. It is aliquoted into sterile septum-capped, 2 ml glass vials and stored at 4°C. rhCC10 is stable under these conditions for at least 14 years and stable at room temperature for at least 18 months. This formulation has been administered by IT instillation in premature infants and by intranasal instillation in healthy adults.

Drug administration: In the previous pilot clinical trial in premature infants, a single dose (1.5 and 5 mg/kg/dose) of rhCC10 was administered by IT instillation within 24 hours of birth in intubated premature infants treated for surfactant deficiency. In the present study, administration of rhCC10 will

be nearly identical to the first clinical trial, however, in the present study the administration of study medication to each lung will be specifically instilled over not less than a 30 second period (duration of instillation not specified in first trial). In addition, just prior to instillation, adjust ventilator settings as follows:

- Increase PIP by 1-2 cm H₂O
- Increase the rate to 35 (if not already there)
- Increase FiO₂ by 5-10%

Dose selection: The IT dose will replicate the single IT doses of 1.5 mg/kg and 5.0 mg/kg from the previous clinical study. Doses will be calculated based on the patient's birth weight.)

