3 OBJECTIVES OF THE STUDY

The purpose of the placebo-controlled study is to determine the efficacy of a single IT dose of rhCC10 (1.5 and 5 mg/kg in a 2 ml/kg fixed volume) in improving survival without CRM as indicated by a reduction in respiratory complications 12 months CGA (using validated respiratory diaries and pulmonary questionnaires, see Appendices D, E, and F). Based on these data, future studies will be designed to determine whether administration of rhCC10 to neonates with RDS is effective in improving survival without CRM.

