6.3 Study Drug Administration

The study drug will be administered to patients within four hours after surfactant administration, but no sooner than 30 minutes after surfactant. Just prior to administration of the study drug, the following adjustments to the ventilator settings should be done: increase the PIP by 1-2 cm H₂O, increase the rate to 35 breaths/min (if not already there) and increase FiO₂ by 5-10%. The study drug should be administered IT in two aliquots. Initially, half the dose will be instilled into one lung (via a pre-measured feeding tube placed into the distal third of the endotracheal tube with the patient in a lateral decubitus position and 30° of Trendelenburg), then the second aliquot will be given into the other lung in a similar fashion. The administration of the study medication to each lung will be specifically instilled over not less than a 30 second period. No further study medication will be provided after the first day of life.

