will be telephone visits by the study coordinator. Visit 13 (5 months CGA) will include explanation of the 6 month 28-day respiratory symptom and quantitative diaries which will be recorded daily (from 5-6 months CGA) for a 4 week period by filling a hard copy of the 28-day diaries. Visit 14 (6 months CGA \pm 2 weeks) will include Visit 6 parameters, review of the 28-day diaries (presence of persistent coughing, wheezing, or use of respiratory medications for 2 days per week for 3 consecutive weeks out of a 4 week diary period is being used to define CRM), eye examination data, parental respiratory questionnaire (illnesses, medications, medical visits, ER visits, hospital admissions for CRM), and safety laboratories. Visit 15-19 (7 months CGA – 11 months CGA) will be telephone visits. Period 2 will end with Visit 20 (12 months CGA \pm 2 weeks) and will include Visit 6 parameters, review of 28-day diaries, hearing screen, parental respiratory questionnaire, and CC10-related study laboratories (see Table 3). Period 3 follow-ups, beyond 12 months CGA, will include Visit 21 (18 months CGA \pm 2 weeks) which includes Visit 6 parameters, 28-day diaries, parental respiratory questionnaire, and Bayley III Infant Neurodevelopmental Exam. Protocols for standardization of all clinical procedures will be included in the study Manual of Operations (MOO). One month before visit 21 (18 month CGA), study coordinators will send the diaries to the parents/guardians and follow-up with a call to verify that these will be completed and brought in for visit 21 (18 month CGA \pm 2 weeks).

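### The syringe content in section 5.3 (1.5–3.1 mL) is 24–25% more than section 3's 2 ml/kg gives for eligible infants (1.2–2.5 mL), and the protocol does not explain the difference

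*Combined protocol and SAP*

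**What the plan says.** Four statements in the combined protocol and SAP bear on the volume.

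- Section 3 (Objectives of the Study) describes the intervention as "a single IT dose of rhCC10 (1.5 and 5 mg/kg in a 2 ml/kg fixed volume". The same volume per kg therefore applies to both dose levels.
- Section 2.2 (Study Drug) sets the weight to be used: "Doses will be calculated based on the patient's birth weight".
- Section 5.1 (Inclusion Criteria) sets the range of that weight: "Birthweight between 600 and 1,250 grams".
- Section 5.3 (Randomization) says that the pharmacy sends "an opaque syringe containing an appropriate dose of the study drug or placebo", that the syringe "will be identified only with the patient Randomization ID number", and that it "will contain 1.5 – 3.1 mL of solution, depending on the birth weight of the patient".

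Section 6.3 (Study Drug Administration) says that "half the dose will be instilled into one lung" and that the second aliquot goes into the other lung. It gives no volume. No ml/kg figure is stated separately for placebo; the syringe range in section 5.3 covers drug and placebo alike.

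**The concern.** The volume per kg and the weight limits are both stated, so the syringe range in section 5.3 should follow by multiplication. It does not. These are the only two statements of the study-drug volume given to an infant, and they differ by about a quarter at both ends of the weight range.

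The volume is an operative part of the treatment: fluid instilled into the trachea of ventilated infants born at 24–29 weeks. As described, the syringe is opaque and carries only the Randomization ID, and section 6.3 gives bedside staff no volume to check against. If the excess is a deliberate overfill, nothing in the protocol says to leave it behind. If it is not, either the 2 ml/kg or the syringe range is wrong.

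**Working it through.** **Inputs.** Volume 2 ml/kg (section 3); birth weight 0.600 to 1.250 kg (sections 2.2 and 5.1); stated syringe content 1.5 to 3.1 mL (section 5.3); stock concentration 5.5 mg/mL (section 2.2).

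**Attempt to reproduce the stated range.** Volume = ml/kg × birth weight in kg.

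| Birth weight | At 2 ml/kg | Section 5.3 | Difference | Ratio | Implied ml/kg |
|---|---|---|---|---|---|
| 600 g | 2 × 0.600 = 1.2 mL | 1.5 mL | +0.3 mL | 1.5/1.2 = 1.25 | 1.5/0.600 = 2.50 |
| 1,250 g | 2 × 1.250 = 2.5 mL | 3.1 mL | +0.6 mL | 3.1/2.5 = 1.24 | 3.1/1.250 = 2.48 |

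The range of 1.5–3.1 mL is not reproduced at 2 ml/kg. It is reproduced at 2.5 ml/kg: 2.5 × 0.600 = 1.50 mL and 2.5 × 1.250 = 3.125 mL, which rounds to 3.1.

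**Possible explanations, tested in turn.**

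1. *Rounding of the mL figures.* A stated 1.5 mL covers 1.45–1.55 mL, so 1.45/0.600 = 2.417 to 1.55/0.600 = 2.583 ml/kg. A stated 3.1 mL covers 3.05–3.15 mL, so 3.05/1.250 = 2.44 to 3.15/1.250 = 2.52 ml/kg. Both ends are met only by 2.44–2.52 ml/kg, which excludes 2.0.
2. *Constant dead-space or priming allowance.* The excess at 600 g is 1.5 − 1.2 = 0.3 mL. Adding 0.3 mL at 1,250 g gives 2.8 mL, which is 0.3 mL short of 3.1.
3. *A different weight range.* At 2 ml/kg, the stated volumes need 1.5/2 = 0.750 kg to 3.1/2 = 1.550 kg. That leaves out eligible infants below 750 g and reaches above the 1,250 g limit.
4. *Undiluted stock.* At 5 mg/kg the volume would be 5 × 0.600/5.5 = 0.55 mL to 5 × 1.250/5.5 = 1.14 mL, well below the stated range. The 1.5 mg/kg dose would need less still.
5. *Proportional overfill.* 1.25 × 1.2 = 1.5 mL and 1.25 × 2.5 = 3.125 mL. This fits. Allowing for rounding, the overfill would be 2.44/2 = 1.22 to 2.52/2 = 1.26, that is 22–26%. The protocol mentions no overfill.

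**What could follow for the dose (assumptions, not findings).** The result depends on which volume the dilution is made for and which is given.

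- Diluted for 2.5 ml/kg and given in full: the mg/kg dose is correct, and the fluid volume is 25% above section 3.
- Diluted for 2 ml/kg, filled to 2.5 ml/kg, and only 2 ml/kg given: both dose and volume are as section 3 states.
- Diluted for 2 ml/kg, filled to 2.5 ml/kg and emptied: 5/2 × 2.5 = 6.25 mg/kg instead of 5, or 1.5/2 × 2.5 = 1.875 mg/kg instead of 1.5.
- Diluted for 2.5 ml/kg but only 2 ml/kg given: 5/2.5 × 2 = 4.0 mg/kg instead of 5, or 1.5/2.5 × 2 = 1.2 mg/kg instead of 1.5.

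Nothing in the protocol indicates which of these applies.

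**The case against.** The strongest reply is that the two figures may describe different quantities. Section 3 gives the volume of the dose; section 5.3 gives what the syringe holds. A syringe filled beyond what is instilled is not in itself a contradiction, particularly when delivery is through a feeding tube. This is possible, and the arithmetic allows a proportional overfill. But section 5.3 presents the syringe as holding the dose, and neither an overfill nor an instruction to leave part of it is stated.

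A second reply is that 2 ml/kg may itself be a rounded figure: 2.44–2.49 ml/kg would round to 2 and fit both ends of the syringe range. That reading is strained, because section 3 calls the volume fixed.

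A third is that the details may sit elsewhere. Section 6.4 says: "Protocols for standardization of all clinical procedures will be included in the study Manual of Operations (MOO". The manual is not among the documents and may well settle what is prepared and given. It would not make sections 3 and 5.3 agree.

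Finally, harm is not shown. Dose is set in mg/kg, the pharmacy receives the birth weight and prepares each syringe individually, and the range is a descriptive remark in the section on randomization. This stands, and it limits the point to an inconsistency in a stated volume. It also means that the correction should follow what the sponsor intends, since changing the wrong figure would introduce an error.

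**Conclusion.** The inconsistency is real. For eligible infants, the syringe content in section 5.3 exceeds the section 3 volume by 0.3 mL (25%) at 600 g and 0.6 mL (24%) at 1,250 g. The stated range corresponds to 2.44–2.52 ml/kg against a stated 2 ml/kg. This rests on taking 2 ml/kg as exact and on the eligible weight range applying to the syringe range. Confidence in the mismatch is high.

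The cause is not established. A range calculated at 2.5 ml/kg and an unstated overfill of about 25% both fit. No error in mg/kg delivered, imbalance between arms, or effect on sample size or analysis is shown. It still merits correction, because it concerns the volume instilled into extremely preterm infants and a reader cannot tell which figure governs.

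**What to change.** The sponsor should confirm what is prepared and what is instilled, then use one ml/kg value in sections 3 and 5.3:

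- If 2 ml/kg is prepared and given, restate the syringe range in section 5.3 as 1.2–2.5 mL. This is the default, since 2 ml/kg is the only volume per kg that the protocol states.
- If 2.5 ml/kg is prepared and given, change section 3 to 2.5 ml/kg.
- If an overfill of about 25% is intended, state it in section 5.3 and add to section 6.3 that only 2 ml/kg is instilled, half to each lung.

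The cost is a one-line correction, plus one sentence in section 6.3 if there is an overfill. Design, sample size and analysis are unaffected.
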